7.3.2 Oral Roflumilast Tablet

Oral roflumilast (DALIRESP®, a 500 µg tablet) has been approved globally for the treatment of COPD and has been evaluated in nine Phase III/IV randomized double-blind clinical trials (Wedzicha 2016). Overall, the safety of oral roflumilast has been well established in its targeted population of mostly middle- and upper-aged individuals who currently smoke cigarettes or have smoked them extensively in the past. Adverse events (AEs) reported with roflumilast tablets have been consistent with those expected for oral PDE-4 inhibitors. In a pooled analysis of safety data from 6-month and 1-year clinical trials (N=8630), the most common AEs were diarrhea, weight loss and nausea. Other AEs reported more frequently with roflumilast treatment than with placebo were back pain, influenza, insomnia and decreased appetite (Michalski 2012, Wedzicha 2016).

In addition to the self-reported cases of weight loss in the 6-month and 1-year oral trials, clinically significant weight loss was also reported in two prospective studies that evaluated weight (Michalski 2012).

Psychiatric-related AEs were also greater in patients treated with roflumilast tablets (5.9%) compared to those treated with placebo (3.3%). The most common psychiatric-related AEs were insomnia, depression and anxiety. A small number of cases of completed suicide and suicide ideation have been reported in patients taking oral roflumilast in clinical trials and also during post-marketing experience (Michalski 2012).

The only contraindication to oral roflumilast, other than hypersensitivity to components of the product, is in patients with moderate to severe liver impairment (Child-Pugh B or C), where systemic levels of roflumilast may become highly elevated.

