10.1.6 Patient Health Questionnaire Depression Scale (PHQ-8)

The 8 item PHQ-8 Assessment (see [Appendix 3](#)) will be performed as follows: Screening, Baseline, Week 1, Week 2, and Week 4.

A subject with a PHQ-8 score of '15' or above should be referred promptly to a mental health care professional and, if currently applying study drug, consideration be given to discontinuation from study drug.

PHQ-8 score is the sum of the responses for the 8 questions.

Five severity categories of depression are defined as follows:

- None – Minimal depression (1 to 4)
- Mild depression (5 to 9)
- Moderate depression (10 to 14)
- Moderately severe depression (15 to 19)
- Severe depression (20 to 27)

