## 2 STUDY OBJECTIVES AND ENDPOINTS

OBJECTIVES	ENDPOINTS
Safety	Safety endpoints
To assess the safety of ARQ-151 cream 0.05% vs ARQ-151 cream 0.15% vs vehicle administered QD x 4 weeks to adolescent and adult subjects with mild to moderate atopic dermatitis.	
 
Incidence of local and non-local treatment-emergent adverse events (TEAEs)
 
Change from baseline in vital signs
 
Change from baseline in clinical laboratory test results
 
Change from baseline in electrocardiograms (ECG)
 
Patient Health Questionnaire – 8 (PHQ-8) and Columbia Suicide Severity Rating Scale (C-SSRS) assessments
 
Local tolerability assessments
 
 
Subset analysis by age group (adolescents and adults) will also be conducted.

Efficacy	Efficacy endpoints
To assess the efficacy of ARQ-151 cream 0.05% vs ARQ-151 cream 0.15% vs vehicle administered QD x 4 weeks to adolescent and adult subjects with mild to moderate atopic dermatitis.	
Primary:
 
 
Change from baseline in Eczema Area and Severity Index (EASI) Total Score at Week 4
 

Protocol Number: AQR-151-212

Sponsor: Arcutis, Inc.

	
Secondary:
 

• Percent change from baseline in EASI Total Score at each study visit

• Change from baseline in EASI Total Score at weeks 1 and 2

• Achievement of a 75% or greater improvement in EASI (EASI75) score from baseline to each study visit

• Achievement of a 50% or greater improvement in EASI (EASI50) score from baseline to each study visit

• Change from baseline in BSA involvement at each study visit

• Change from baseline in WI-NRS pruritus score at each study visit

• Achievement of a <math>\geq 4</math>-point improvement from Baseline in WI-NRS pruritus score at each study visit for subjects with a Baseline WI-NRS <math>\geq 4</math>

 
Subset analysis by age group (adolescents and adults) and baseline EASI score ('2' (mild) or '3' (moderate)) will also be conducted.

Pharmacokinetic	Pharmacokinetic endpoints (not covered in this SAP)

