## 5.5 Descriptive Statistics

All continuous variables will be summarized by presenting the number of subjects, mean, SD, median, minimum, and maximum. Categorical variables will be presented as frequencies and percentages. Summary tables will be presented by treatment and visit, when applicable.

Change from baseline will be calculated as:

Assessment value at post-baseline visit X – Baseline value.

Percent change from baseline will be calculated as:

(Assessment value at post-baseline visit X – Baseline value) / Baseline value \* 100.

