## 13.2 Clinical Laboratory

Descriptive statistics will be presented for data related to chemistry, hematology, and urinalysis. Change from baseline values will be presented for each post-baseline assessment. Frequencies and percentages for each result will be provided for qualitative urinalysis data.

Shift tables from baseline to the worst post-baseline assessment describing shifts to abnormality will be provided as well. Only subjects with a baseline result and a post-baseline result for the parameter will be considered.

Separate listings of all data for chemistry, hematology, urinalysis, and pregnancy tests will be provided.

Laboratory data will be presented in SI units.

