### **13.6 Patient Health Questionnaire Depression Scale (PHQ-8)**

The Patient Health Questionnaire Depression Scale is an 8 question Assessment (see [Appendix 5](#)).

The PHQ-8 score is the sum of the responses for the 8 questions, each question ranging from 0 (Not at all) to 3 – (Nearly every day). Five severity categories of depression are defined as follows:

- None – Minimal depression (1 to 4)
- Mild depression (5 to 9)
- Moderate depression (10 to 14)
- Moderately severe depression (15 to 19)
- Severe depression (20 to 24)

The score will be set to missing in case of at least one missing value. The PHQ-8 score will be summarized by treatment and visit. Furthermore, the frequency of subjects within each severity category will be summarized by treatment and visit.

 INNOVADERM RESEARCH INC.	STATISTICAL ANALYSIS PLAN, Final V1.0Final 1.0
Protocol Number: AQR-151-212	Sponsor: Arcutis, Inc.

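### PHQ-8 is planned only as by-visit scores and category counts, so the outputs cannot show how many subjects newly reach 15 or more, or worsen by a category

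*SAP*

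**What the plan says.** SAP 13.6 plans two outputs. The first is the score: "The PHQ-8 score will be summarized by treatment and visit". The second is the categories: "Furthermore, the frequency of subjects within each severity category will be summarized by treatment and visit". The section names no change from baseline, shift table or listing.

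No other section supplies them:

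- The SAP section 2 endpoint table labels vital signs, laboratory tests and ECG as changes from baseline. The entry for this scale reads only "Patient Health Questionnaire – 8 (PHQ-8) and Columbia Suicide Severity Rating Scale (C-SSRS) assessments".
- SAP 5.5 defines change from baseline ("Assessment value at post-baseline visit X – Baseline value") but does not assign it to any variable.
- Protocol 11.1.3 and 11.3 do not mention PHQ-8.

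A baseline value exists. Protocol 10.1.6 says the assessment "will be performed as follows: Screening, Baseline, Week 1, Week 2, and Week 4". The same section sets an action threshold for the individual subject: at 15 or above the subject is to be referred and, if on treatment, "consideration be given to discontinuation from study drug". Protocol 9.7 and 10.9 use the same threshold.

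**The concern.** The protocol uses PHQ-8 subject by subject, while the SAP reports it only as arm totals at each visit. The scale has a reason to be in this trial: Protocol 7.3.2 reports more psychiatric adverse events on oral roflumilast than on placebo (5.9% against 3.3%), with depression among the most common.

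The natural safety question is how many subjects per arm were below 15 at baseline and reached 15 or more on treatment, or moved up a category. Totals by visit cannot answer it if some subjects enter with raised scores. Exclusion criterion 11 bars a known or suspected history of severe depression or suicidal ideation within 5 years, but no entry criterion sets a PHQ-8 limit.

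**Working it through.** **No figure to reproduce.** The plan states no number for PHQ-8 analysis. The check has three parts: what neighbouring sections plan, what by-visit counts can identify, and which records can drop out.

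**1. Planned outputs side by side (SAP 13.2 to 13.7)**

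| Assessment | Change from baseline | Shift table | Listing |
|---|---|---|---|
| Laboratory (13.2) | yes | yes | yes |
| Vital signs (13.3) | yes | weight only | yes |
| ECG (13.4) | yes | yes | yes |
| Local tolerability (13.5) | no | no | yes |
| PHQ-8 (13.6) | no | no | no |
| C-SSRS (13.7) | no | no | yes, plus one of subjects with any positive answer |

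The laboratory wording shows the kind of output that is missing: "Shift tables from baseline to the worst post-baseline assessment describing shifts to abnormality will be provided as well". PHQ-8 is the only row with no subject-level output.

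**2. What by-visit counts identify**

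Let an arm have n subjects with complete data, a of them at or above a cut-off at Baseline and b at Week 4. The number who are at or above it at Week 4 but were not at Baseline lies between

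- lower limit: max(0, b − a)
- upper limit: min(b, n − a)

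The arm size of 30 to 35 is from SAP 5.1. The documents give no PHQ-8 counts, so a and b are assumed:

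| n | a | b | New cases possible | Share of arm |
|---|---|---|---|---|
| 35 | 2 | 2 | 0 to 2 | 0% to 5.7% |
| 35 | 4 | 4 | 0 to 4 | 0% to 11.4% |
| 30 | 4 | 4 | 0 to 4 | 0% to 13.3% |
| 35 | 4 | 5 | 1 to 5 | 2.9% to 14.3% |

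For the second row: max(0, 4 − 4) = 0, min(4, 35 − 4) = 4, and 4/35 = 11.4%.

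When b is no larger than n − a, the width of the range is b − max(0, b − a) = min(a, b). The ambiguity is therefore set by how many subjects are already above the cut-off at baseline. With a = 0 it vanishes and the Week 4 count is exact. Because the number at or above a cut-off can only grow as the cut-off is lowered, movement between the milder categories is identified no better at baseline than movement across 15, and probably worse.

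**3. Records that can drop out**

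Protocol 10.5 repeats the Week 4 procedures, including PHQ-8, at early termination. SAP 5.6 maps that visit to the windows in SAP 5.4, where Days 2 to 11 belong to Day 8 and Days 12 to 21 to Day 15. If two assessments fall in one window, the one closer to the target day is used. Take a scheduled visit on Day 8 and termination on Day 11. The distances are 0 and 3 days, so the Day 8 score is kept and the termination score is not summarised. The general listing commitments in SAP 5.6 cover retests and unscheduled visits, and 13.6 has no listing, so the termination score appears in no PHQ-8 output.

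**The case against.** The other side has four fair points.

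- **Net movement is visible.** A reader might infer that the planned tables would hide newly emergent depression altogether. The documents do not support that. If more subjects reach 15 than leave it, the category count rises. Exclusion 11 and the investigator's judgement of good health (inclusion 10) should also keep the baseline count at 15 or more small, and the ambiguity cannot exceed that count at a given visit. This stands, and it limits the size of the point.
- **Adverse events are a parallel route.** SAP 13.1 classes new or worsened events as treatment-emergent, tabulates them by arm and lists them. A depression event recorded this way would be separated from pre-existing illness. This stands in part: no text makes a rise in PHQ-8, or a score of 15, an adverse event.
- **The plan contradicts nothing.** The protocol promises no particular PHQ-8 analysis, and local tolerability and C-SSRS have no change or shift output either. True, but both have listings, from which individual courses can be read.
- **Table shells may add outputs.** SAP section 5 places the layouts in a separate document. They may do so, but the SAP does not commit to it.

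**Conclusion.** The point holds as a reporting gap. The planned PHQ-8 outputs give net movement by arm. They do not identify how many subjects newly reached 15 or more or worsened by a category, and a score displaced by the windowing rule would not be seen in them. The algebra needs no distributional assumption. The counts put into it are assumed, and the ranges of 0 to 4 or 1 to 5 new cases illustrate the limit and do not forecast results.

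Two stronger readings should be resisted. A reader might turn the oral rates of 5.9% and 3.3% into expected PHQ-8 cases per arm. Those are rates of all psychiatric adverse events with tablets, including insomnia and anxiety, and not of scores of 15 or more over 4 weeks of a cream. A reader might also infer that relief of itch would lower scores in the active arms and bias the comparison towards no signal. No passage supports that effect, and SAP section 13 plans no inferential comparison of safety data.

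This is an inexpensive improvement to how a safety scale is reported. It does not affect the efficacy conclusions.

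**What to change.** In SAP 13.6 add, by treatment arm:

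- (a) a shift table of PHQ-8 category from baseline to worst post-baseline score, using all post-baseline records, including early-termination scores that the windowing rule would set aside;
- (b) the number of subjects with a baseline score below 15 and any post-baseline score of 15 or more;
- (c) a by-subject PHQ-8 listing.

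Change from baseline by visit is optional.

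Two details must be settled before the shift table can be programmed. The lowest category starts at 1, so a score of 0 has no cell; assign it to that lowest category. Section 13.6 sets the score to missing if any item is missing, while SAP Appendix 5 does so only if more than one is. Reconcile these and state one rule.

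The cost is SAP wording, one or two tables and a listing. All the data are already collected. The action threshold of 15 is taken from the protocol as it stands, and no referral or discontinuation rule changes.

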### **13.7 Columbia-Suicide Severity Rating Scale (C-SSRS)**

The Columbia-Suicide Severity Rating Scale (C-SSRS) is a questionnaire used for suicide assessment developed by multiple institutions, including Columbia University (see [Appendix 6](#)). A listing of the C-SSRS assessments will be provided. In addition, a listing of data will be provided for all subjects who answer 'Yes' to any question on the C-SSRS questionnaire.

 INNOVADERM RESEARCH INC.	STATISTICAL ANALYSIS PLAN, Final V1.0Final 1.0
Protocol Number: AQR-151-212	Sponsor: Arcutis, Inc.

## 14 APPENDICES

---

### Appendix 1 Output Conventions

TLF will be generated using SAS® and will be displayed on letter size paper with landscape orientation, 1-inch margins, and 9 pt Courier New font.

The header section will comprise the sponsor's name, the protocol number, the delivery description, the data cut-off date (if applicable), the TLF number, the TLF title, the analysis population, and the page number (Page X of Y). The footer section will include the TLF footnotes, the CRO's name, the date and time of the execution of the program, the reference listings and the name of the program.

P-values equal to and above 0.001 will be reported to 3 decimal places; p-values less than 0.001 will be reported as “<0.001”; p-values greater than 0.999 will be reported as “>0.999”.

The mean, median, and quantiles will be displayed to one more decimal place than the original value; minimum and maximum will keep the same number of decimal places as the original value; SD, standard error, and CI will be displayed to two more decimal places than the original value. If derived parameters are to be summarized, the number of decimals of the derived values is to be chosen on a case-by-case basis, but the rule above applies.

For categorical summary tables, percentages will be reported to one decimal place. Percentages between 0 and 0.1 (both exclusive) will be displayed as “<0.1”. The denominator for each percentage will be the number of subjects within the population per treatment group unless otherwise specified.

Listings will be ordered by treatment group, subject number, date, and visit (where applicable). Imputed dates and imputed missing data will not be presented in the listings.

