11.1 Statistical Methods

The methodology presented below is a summary of the more detailed analysis plan that will be presented in the Statistical Analysis Plan (SAP). The SAP will be finalized before the database is locked and unblinded. Any changes to the methods described in the final SAP will be described and justified in the clinical study report.

All statistical processing will be performed using SAS[®] (Version 9.4 or later) unless otherwise stated. No interim efficacy analyses are planned.

Descriptive statistics will be used to provide an overview of the safety, efficacy, and pharmacokinetic results. For categorical parameters, the number and percentage of subjects in each category will be presented. The denominator for percentage will be based on the number of subjects appropriate for the purpose of analysis. For continuous parameters, descriptive statistics will include n (number of subjects), mean, standard deviation (SD), median, minimum, and maximum.

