### 6.2 Handling of Dropouts or Missing data

See [Appendix 2](#) for handling of completely or partially missing dates for prior and concomitant medications and adverse events.

The primary method of handling of missing data will be the MMRM method without explicit imputations for missing data. A sensitivity analysis will be carried out on the primary endpoint using the last observation carried forward (LOCF) as an imputation for missing data. Only post-baseline values will be carried forward.

For secondary endpoints involving proportions, missing data at any post-baseline assessment will be imputed using LOCF and they will then be determined as a responder or non-responder based on the LOCF value.

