## 13.5 Local Tolerability Assessments

Investigator Local Tolerability Assessments

 INNOVADERM RESEARCH INC.	STATISTICAL ANALYSIS PLAN, Final V1.0Final 1.0
Protocol Number: AQR-151-212	Sponsor: Arcutis, Inc.

Local tolerability assessed by the investigator will be summarized by treatment and visit for dermal response on an 8-point scale (0-7). Furthermore, the frequency of subjects with each dermal response score as well as other effects (A to G) will be summarized by treatment and visit.

A sensitivity analysis of investigator local tolerability assessments will be conducted in which data from study sites 19, and 21 will be excluded. Due to a misunderstanding of the data collection form, data from both of these sites were initially assessed as disease assessments rather than local tolerability assessments. Data were updated after correct understanding of the CRF was attained, however, the effect of this post facto update of these data will be evaluated with this sensitivity analysis.

A listing of investigator local tolerability assessments will be provided.

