#### Subject Local Tolerability Assessments

Local tolerability assessed by the subject will be summarized by treatment and visit for tolerability grading on a 4-point scale (0-3). Furthermore, the frequency of subjects with each tolerability score will be summarized by treatment and visit.

A listing of subject local tolerability assessments will be provided.

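### By-visit tolerability, PHQ-8 and urinalysis percentages default to the whole arm as denominator, so they shrink with every missed assessment

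*SAP*

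**What the plan says.** SAP Appendix 1 (Output Conventions) gives the rule for categorical summary tables: "The denominator for each percentage will be the number of subjects within the population per treatment group unless otherwise specified". SAP 5.5 adds that "Categorical variables will be presented as frequencies and percentages", by treatment and visit where applicable.

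The by-visit safety tables are described without a denominator:

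- SAP 13.5, investigator assessment: "the frequency of subjects with each dermal response score as well as other effects (A to G) will be summarized by treatment and visit".
- SAP 13.5, subject assessment: "the frequency of subjects with each tolerability score will be summarized by treatment and visit".
- SAP 13.6, PHQ-8: "the frequency of subjects within each severity category will be summarized by treatment and visit". The same section says of the PHQ-8 score: "The score will be set to missing in case of at least one missing value".
- SAP 13.2 asks for frequencies and percentages of each qualitative urinalysis result.

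Elsewhere the SAP does specify otherwise. Section 7.1 gives separate denominators for screen failures and discontinuations. Sections 13.2 and 13.3 limit the laboratory and weight shift tables to subjects with both results.

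Protocol 11.1 is looser: "The denominator for percentage will be based on the number of subjects appropriate for the purpose of analysis".

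On missing data, SAP 6.2 states: "For secondary endpoints involving proportions, missing data at any post-baseline assessment will be imputed using LOCF". The vIGA-AD proportions are exploratory (SAP 12.3), so that sentence does not reach them, and no other rule is given for them.

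**The concern.** A by-visit percentage is read as the share of subjects examined at that visit who had the finding. With the whole arm as denominator, it mixes two things: how common the finding was, and how many subjects were seen. At later visits, when more subjects have left, the percentage falls even if the rate among those examined is constant. If one arm loses more subjects than another, equal rates look different.

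Safety is part of the primary objective and has no formal inference (SAP 13), so the displayed percentages are what a reader will use to compare tolerability between arms. The authors restricted the laboratory and weight shift tables to subjects with data, but no equivalent sentence covers the by-visit category tables.

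For vIGA-AD the question is narrower. The displayed percentage would use all randomized subjects by default, whereas a CMH test run on observed scores would use only subjects with a score. The table and its p-value could then describe different subjects.

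**Working it through.** **Inputs.** Arm size 30-35, dropout 10-25% and 27 evaluable per arm come from SAP 5.1. The documents give no tolerability, PHQ-8 or urinalysis rates, so the category counts and rates below are assumptions.

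**The plan's own figure first.** Standardized difference = 35/40 = 0.875. A two-sample t-test at two-sided 0.025 (Bonferroni for two comparisons) with 80% power needs 26.1, so 27 per arm; power at 27 is 81.5%. Dropout inflation: 27/0.90 = 30 and 27/0.75 = 36, against the stated 30-35. The range reproduces to within one subject, so it is a fair guide to the missingness the plan expects.

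**Effect of the denominator.** Let x be subjects in a category, m subjects assessed at the visit and N the arm's population.

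Displayed = x/N = (x/m) × (m/N)

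If nobody who drops out has an assessment mapped to the visit, m/N = 1 − dropout, which is 0.90 at 10% and 0.75 at 25%.

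| N | Assessed m | Category count x (assumed) | Whole arm x/N | Assessed x/m |
|---|---|---|---|---|
| 30 | 27 (10% missing) | 5 | 16.7% | 18.5% |
| 35 | 26 (about 25% missing) | 5 | 14.3% | 19.2% |

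**Unequal missingness (illustration only; the split is assumed and is not in the plan).** Suppose the rate among assessed subjects is 20% in both arms, with 25% missing in one and 10% in the other:

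- Finding present: 0.20 × 0.75 = 15.0% against 0.20 × 0.90 = 18.0%, a 3-point artefact.
- Finding absent (grade 0): 0.80 × 0.75 = 60% against 0.80 × 0.90 = 72%.

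Both rows shrink, so the arm with more missing data looks better on the finding and worse on grade 0. Neither comparison is valid.

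**What limits the loss at a visit.**

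- Protocol 10.5 asks for Week 4 procedures at early termination, and SAP 5.6 maps them by the windows in 5.4. An exit visit on Days 22-32 supplies Week 4. An earlier one supplies Week 1 or 2 and leaves Week 4 empty.
- Subject burning/stinging is collected at Baseline, Week 1 and Week 2 only (Protocol 10.1.8), so Week 4 dropout does not touch it.
- In the other direction, one missing PHQ-8 item removes the score (SAP 13.6), so PHQ-8 missingness can exceed dropout.

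**The case against.** The strongest reply has five parts.

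*The rule is only a default.* This is correct. A reader might infer that every percentage in the report is affected, and the documents do not support that. Sections 7.1, 13.2 and 13.3 set exceptions, and LOCF fills most missing values for the secondary proportions. The point is confined to the tables named above.

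*Missing subjects are not counted as free of the finding.* Also correct. They are placed in no row, so all rows shrink together, and on a single-choice scale the rows add to less than 100%, which an attentive reader could notice. That signal is weaker for PHQ-8, because the listed categories start at 1 and a score of 0 falls in none of them even with complete data.

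*The assessed n appears elsewhere.* Partly so. SAP 5.5 gives n for continuous summaries, and the tolerability and PHQ-8 scores are also summarized by visit. Qualitative urinalysis has no such companion. A reader should not have to recompute a percentage from another summary.

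*The table layouts are in a separate document* (SAP 5), which could set visit-level denominators or a missing row. This cannot be checked here. If that document is silent, Appendix 1 decides.

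*The consequence is modest.* Protocol 11.3.1 rests safety mainly on treatment-emergent adverse events, for which population N is right. This limits the weight of the point but does not remove it.

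Two further inferences should be resisted. The SAP does not contradict Protocol 11.1, whose wording is permissive and fixes no number. Nor is vIGA-AD the same fault: dividing successes by all randomized subjects works like counting missing as non-response, which is defensible, and an observed-case denominator would be a debatable preference.

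**Conclusion.** The point holds for the by-visit tables of investigator and subject local tolerability, PHQ-8 severity category and qualitative urinalysis. Following the SAP as written, each displayed percentage is the assessed-subject percentage multiplied by the fraction assessed: 0.90 to 0.75 if 10-25% of the arm is missing at that visit, and closer to 1 where early-termination data fill the window. Rates are understated relative to subjects actually examined, and are not comparable between arms when missingness differs. The 15.0% against 18.0% example rests on an assumed 20% rate and an assumed 25%/10% split. The plan's 10-25% is one range for sizing the study and predicts no difference between arms.

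For the exploratory vIGA-AD proportions, only a possible mismatch between the displayed percentage and the subjects in the CMH test survives, because no missing-data rule is stated.

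No primary or secondary efficacy conclusion depends on this. It should still be corrected, because the stated rule itself produces the distorted rates.

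**What to change.** 1. In SAP Appendix 1, state that by-visit categorical safety percentages use the number of subjects with a non-missing assessment at that visit, and display that n in each column. Keep population N for adverse events, medications and disposition, except where 7.1 states otherwise.
2. In SAP 12.3, state one missing-data rule for the vIGA-AD proportions and apply it to both the displayed percentage and its CMH test. Extending the LOCF rule already used for the secondary proportions would do this and keep the two sets of endpoints consistent.

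The cost is a sentence or two in the SAP and matching edits to the table shells, with no new data. The change makes the denominator honest. It does not correct for subjects who leave because of poor tolerability, so the displayed n should be read alongside the discontinuation reasons.
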